D. Investigator Experience - [name] is an experienced pediatrician and Associate Professor in the Department of Pediatrics at the University of North Texas Health Science Center (UNTHSC) with ample research interest and background in investigating obesity and type 2 diabetes in children. She has conducted several clinical trials and research studies involving children, has published in peer reviewed journals. Thus, she is experienced with conducting research in a clinical setting. She will be collaborating with [name], Chair and Professor of Pediatrics, UNTHSC and two researchers from Texas Woman's University (TWU)—Drs. [name] and [name]. [name] has about 40 years of clinical and research experience and has published about 100 articles in peer reviewed journals. [name] has a long background as a pediatric dietitian and has worked with parents of infants providing counseling and advice for over 17 years. She also has past experience conducting survey-based research. [name] is a Certified Health Education Specialist and a Certified Health and Wellness Coach who has over 28 years of experience in health education and health promotion, including presentations and publications on child and adolescent health. [name] also has experience conducting both quantitative and qualitative research. Drs. [name] and [name] will be working with experts in research methods from the Center for Research Design and Analysis at TWU.

E. Experimental Design and Methods -

1) *Methods and Procedures* - Thirty to 40 parent/infant dyads/triads of infants aged 3-30 days (15 to 20 parent/infant dyads in each group) will be recruited from the UNTHSC Pediatric Clinic.

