Parents will be screened to be sure they qualify to participate in the study (See attached Screening Form). Parent(s) will read, have the opportunity to ask questions about, and sign the informed consent form and the HIPPA Authorization Form. Each parent who agrees to participate will complete a Participant Information Form with information about their own height, weight, age, race/ethnicity, primary language, and family history. They will also provide the phone number to their mobile device on the data collection sheet, their child's date of birth, and indicate if they will be answering the surveys since only one parent will be permitted to answer the surveys. To participate, at least one parent must agree to answer the surveys. Then, the participants will be randomized to one of the following groups: feeding text messaging or usual care with safety text messaging. A computer-generated blocked randomization schedule with balanced distribution with regards to sex will be used to place

infants into groups. This stratified allocation will be concealed in opaque, sequentially-numbered sealed envelopes, and opened by study staff. While parents recruited may vary in weight status, income, and race/ethnicity, in a pediatric primary care setting randomizing participants into groups based on these multiple criteria, which are not gathered on parents of patients would be burdensome for clinic staff. Thus, parent participants will be randomized into each study group (usual care or text-messaging) based only on sex of the infant.

After research staff know the group assignment, they will enroll parents into the study using the child’s date of birth and the parents’ mobile phone numbers. See the figure below for the sequence of enrollment events.

[figure not shown]

Figure 1: Flow and Sequence of Enrollment Events

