Texas Health Steps is the recommended schedule for well visits with a pediatric healthcare provider for patients enrolled in Texas Medicaid. The following visits are recommended: 3-5 days, 2 weeks, 2 months, 4 months, 6 months, 9 months, 12 months, 15 months, 18 months, and 2 years. Insurance companies allow well visits at the same interval. Not all parents are able to bring children according to this precise schedule; thus, slightly flexible age ranges will be used for each data collection. The project proposes to gather data from both groups of parents only between 3-30 days, 2-4 months, 6-9 months, and 12 months so that parents who miss attending one of the scheduled visits can be caught at the next one. To track feeding practices, at the 0-30 day, 2-4 month, 6-9 month, and 12 month visits, parents will be given a link to answer questions in a mobile survey in PsychData adapted from the National Health and Nutrition Examination Survey Diet Behavior Nutrition Questionnaire⁵⁷ with additional questions on responsive feeding practices from the Infant Feeding Style Questionnaire (IFSQ)⁵⁸⁻⁵⁹. This link will also be sent by text if the survey is not filled out at the scheduled visit. To track actual intake, one of the research staff will call parents of infants between 2-4 months, 6-9 months, and at 12 months to conduct a 24-hour recall of the infant’s intake. The Healthy-Txt messaging system captures only the data specified by the research protocol. For this study, Healthy-Txt will gather data on whether participants opt out of participation, responses to yes or no questions in the text messages, and whether participants access landing page information. This data is linked to the participants’ (parent’s) mobile phone number. Finally, a chart review of each participating infant’s chart (part of the participating parent/infant dyad) will be conducted by one of the research staff employed at the UNTHSC pediatric clinic. The research staff will keep a master list of the infant’s medical record number (MRN) and a randomly assigned participant ID number. They will use this master list to collect the following data from the infant’s chart: age, weight, and height at 0-30 days, 2-4 month visit, 6-9 month visit, 12 month visit.

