The information on the infant's age, weight, and height gathered from the electronic medical record (EMR) will be stored in a spreadsheet together with the randomly assigned participant ID number. No identifying information will be stored together with the MRN on the master list. The master list will be stored on a secure drive in the UNTHSC department of pediatrics. Only the PI, and the research coordinator will have access to the master list. The de-identified spreadsheet with the infant age, height, and weight data will be shared with the TWU collaborators and research staff for analysis. Information from the 24-hour recall will be recorded on a data collection form with only the randomly assigned participant ID number and when analyzed will be stored in a spreadsheet with only the randomly assigned participant ID number. The co-investigators, together with [name], will be responsible for analyzing the data with assistance from statisticians in the Center for Research Design and Analysis at Texas Woman's University.

Descriptive statistics will be used to describe mean, median, standard deviation, and range for all continuous variables in each group. Frequency and percentage will be calculated to demonstrate categorical variables in each group. Then, independent t tests will be conducted to compare continuous demographic variables between the two groups, and cross-tabulation using chi-square test will be used to compare categorical demographics between the two groups. The relationships between demographic variables and baseline outcomes will also be examined to identify whether any demographic variables need to be controlled for in the primary analyses. In addition, feeding practices will be compared between the two groups using repeated measures analysis of variance (ANOVA) or repeated measures analysis of covariance (ANCOVA). All data will be analyzed using IBM SPSS, version 25, and a $P < 0.05$ is considered significant. The number of participants in part two was determined using a moderate effect size ($f = 0.25$) with 0.8 power to detect a difference between the two groups. With repeated measures ANOVA (2 groups x 3 time points), a total of 37 participants including a 30% drop out rate were required for adequate power.

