5) Describe plans for *recruitment of subjects*. Parents will be recruited during the first few in-office visits with their infant's healthcare provider. One of the students or the Research Coordinator will visit with interested parents, explain the consent form, answer questions about the study, and get consent. Those participants who decide to participate will be randomized into the control or intervention group at that time. They will fill out a basic information form including their cell phone numbers so that they may begin receiving text messages.

G. Risk/Benefit Assessment

1) This is a minimal risk project that involves providing basic information about feeding to parents of infants either through handout (control group) or text message (intervention group) and basic information about infant safety through text message (control group) or handout (intervention group). There is no direct benefit of participation to subjects other than a possible gain in knowledge and awareness about early nutrition, infant feeding practices (intervention), and infant health and safety guidelines (control).

2) Because the study is expected to provide useful information to parents of infants in a format that is convenient and acceptable to them, the minimal risk is considered acceptable.

3) This method of conducting research is at least as favorable as that provided by providing handouts because it is convenient. In preliminary research involving focus groups, all parents participating reported being willing to receive text messages with feeding advice.

4) Describe any potential RISKS OR DISCOMFORTS in detail.

There is a potential financial risk because carrier message and data rates may apply. Participants will be advised of this risk but will also be receiving incentives to help compensate for any potential financial risk.

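### Covariates for the primary analyses are to be picked from the trial's own baseline data, while infant sex (the only stratum) and the 0-30-day values are not fixed in the model and the first survey may be answered after texts begin

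*Protocol*

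**What the plan says.** Section E.2 first compares demographics between the randomised groups with t tests and chi-square tests. For the primary analyses, it then states that "relationships between demographic variables and baseline outcomes will also be examined to identify whether any demographic variables need to be controlled for". Feeding practices are to be compared by repeated measures ANOVA or ANCOVA. No covariate, candidate list or selection threshold is given beyond the general statement that "a $P < 0.05$ is considered significant".

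Section E.1 makes infant sex the only stratification factor: parents are "randomized into each study group (usual care or text-messaging) based only on sex of the infant". It also collects the feeding survey and the infant's weight and length at 0-30 days. The 24-hour recall starts only at 2-4 months.

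On timing, section F.5 says: "Those participants who decide to participate will be randomized into the control or intervention group at that time". The parent's information form then allows texts to begin. The enrolment steps described in E.1 run from consent to the information form to randomisation and do not mention the survey. Section E.1 says of the surveys: "This link will also be sent by text if the survey is not filled out at the scheduled visit". Section E.4 expects surveys at office visits but also accepts answers after the appointment.

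**The concern.** There are three linked weaknesses.

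- **Selection rule.** The adjustment set depends on what the baseline data happen to show, and on a judgement that the protocol does not define. A covariate earns its place by predicting the follow-up outcome, which should be known beforehand. Relation to the baseline outcome is only a rough substitute.
- **Known covariates left out.** Sex is balanced by design. If it is prognostic and omitted, the standard error is overstated. The outcome's own 0-30-day value is often the best available predictor and is already collected, yet neither term is fixed in the model. The sample size assumes three time points while four surveys are planned, so the role of the first survey is unsettled.
- **Order of events.** A baseline answered after feeding texts have started is a post-randomisation measurement. Adjusting for it can remove part of the effect under study.

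At stake are precision and a pre-fixed comparison in a very small trial.

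**Working it through.** **The plan's own figure.** Section E.2 was "determined using a moderate effect size ($f = 0.25$) with 0.8 power to detect a difference between the two groups", and continues: "With repeated measures ANOVA (2 groups x 3 time points), a total of 37 participants including a 30% drop out rate were required". For the group-by-time test, lambda = f² × N × m / (1 − rho), with df 2 and 2(N − 2). The correlation between repeated measures is not stated; take rho = 0.5 and sphericity. With N = 28 and m = 3, lambda = 0.0625 × 28 × 3 / 0.5 = 10.5, df are 2 and 52, and power is 0.812. Then 28 × 1.3 = 36.4, rounded up to 37, which is the plan's figure. The illustration below therefore uses N = 28.

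**Selection against baseline.** No threshold or candidate list is stated. Assume a screen at 0.05 on 6 to 8 independent, uninformative demographics. The chance of at least one selection is 1 − 0.95^6 = 0.26 to 1 − 0.95^8 = 0.34 per outcome. For a demographic truly correlated at 0.3 with the baseline outcome, n = 37, Fisher's z gives atanh(0.3) × √34 = 0.3095 × 5.831 = 1.80, and power = Phi(1.80 − 1.96) = 0.44. A useful covariate would be missed more often than found.

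**Omitting sex.** If sex explains 5% of the variance (assumption), the unadjusted test runs at 2 × (1 − Phi(1.96 / √0.95)) = 0.044 instead of 0.05. This is slightly conservative.

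**Simulation.** 8,000 runs per scenario; 28 dyads, 14 of each sex, allocated 1:1 within sex; one follow-up summary; sex effect 0.5 SD; eight pure-noise demographics selected at p < 0.05 against baseline. All settings are assumptions, including the true effect of 0.8 SD. The ranges or triples are for baseline correlations of 0.3, 0.5 and 0.7.

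| Model | Type I error | Power |
|---|---|---|
| Unadjusted | 0.044-0.046 | 0.50, 0.50, 0.51 |
| Demographics selected against baseline | 0.043-0.047 | 0.50, 0.50, 0.52 |
| Sex only | 0.049-0.052 | 0.53, 0.53, 0.53 |
| Sex and baseline | 0.051-0.055 | 0.54, 0.63, 0.80 |

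Monte Carlo error is about √(0.05 × 0.95 / 8000) = 0.002 for type I error and √(0.25 / 8000) = 0.006 for power. The selection route is thus hardly distinguishable from no adjustment. That follows in part from the noise covariates; a truly prognostic demographic would help somewhat when it was picked.

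The gain agrees with theory. The unadjusted standard error is 2/√28 = 0.38. Multiplying by √(1 − r²) gives 0.36, 0.33 and 0.27; the simulation gives 0.37, 0.34 and 0.28, slightly larger because of chance imbalance.

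These gains concern the comparison of groups on a follow-up value. A covariate constant over time does not sharpen the group-by-time test unless its own interaction with time is also fitted.

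**Late baseline.** If texts have already shifted the baseline by a fraction c of the effect delta, the adjusted analysis estimates delta × (1 − rho × c), where rho is here the baseline correlation. With rho = c = 0.5 (assumed), this is 1 − 0.25 = 0.75 of the effect, or 25% too small.

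**The case against.** Naming covariates is ordinarily left to a statistical analysis plan. ANCOVA remains available, and sex could enter if it counts as a demographic. That is fair as far as it goes, but the protocol does not stay silent: it states a data-driven rule, which a later plan would inherit.

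A reader might infer that the rule inflates the false-positive rate. The documents do not support that. The rule as written uses demographics and baseline outcomes, not follow-up results, and simulated type I error stays at 0.043-0.047. Nor are the between-group t and chi-square tests said to drive covariate choice; only the baseline-outcome sentence does so. Choosing covariates by their relation to this trial's follow-up data would be worse.

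A reader might also take the 26-34% as a property of the plan. It is not: E.2 speaks of examining relationships and sets no cut-off, and items such as parental height and weight are unlikely to be independent. A false pick costs a degree of freedom and does not bias a randomised comparison.

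Finally, a reader might infer that the baseline will be contaminated. E.4 expects completion in the office, the texted link is a fallback for all four surveys, and the enrolment figure in E.1 is not shown and may put the survey first. Late completion is a possibility that the visible text permits, and no more.

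**Conclusion.** The point stands as one of efficiency and pre-specification. The selection rule brings discretion and little or no precision. It does not bias the comparison or raise type I error, provided covariates are chosen without sight of follow-up. The protocol does not state that proviso, and the timetable in E.6 runs analysis alongside data collection.

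Omitting sex costs little: 0.044 against 0.05 if it explains 5% of the variance. The value of baseline adjustment depends on a correlation that the documents do not give. Beyond sex alone, power moves only from 0.53 to 0.54 at 0.3, but to 0.63 at 0.5 and 0.80 at 0.7, for 28 dyads and a 0.8 SD effect. The attenuation from a late first survey is conditional on its happening, and its size rests on assumed values.

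Baseline adjustment does not apply to every outcome. The 24-hour recall has no 0-30-day value, and solids and sugary drinks will barely vary at that age. With "15 to 20 parent/infant dyads in each group", the change is still worth making because it costs almost nothing.

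**What to change.** - **Model.** Delete the step that selects covariates from the data. Fix the repeated measures model in advance as group, time, group-by-time, infant sex, and the outcome's own 0-30-day value where one exists and varies. That covers the weight-for-length z score from the chart and suitable survey scores. For the 24-hour recall and for practices nearly constant at 0-30 days, adjust for sex only. Where the 0-30-day value is a covariate, let time consist of the follow-up visits, so that it is not used twice.
- **Timing.** State that the first survey is to be completed before the envelope is opened.
- **Late or missing first survey.** Keep the dyad in the analysis and treat the baseline as missing, handled by a simple pre-stated method such as mean imputation of the covariate. Dropping such dyads could cost more than the adjustment gains.

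The cost is a change of wording, one or two degrees of freedom, and a few minutes at the enrolment visit.

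### The repeated measures ANOVA/ANCOVA fixed for feeding practices discards partly observed dyads and ignores age within visit windows; a mixed model recovers a modest amount of precision at little cost

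*Protocol*

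**What the plan says.** Section E.2 (Data Analysis and Data Monitoring) names the method for feeding practices: "feeding practices will be compared between the two groups using repeated measures analysis of variance (ANOVA) or repeated measures analysis of covariance (ANCOVA"). The only covariates it considers for adjustment are demographic variables found to be related to baseline outcomes. It adds that "All data will be analyzed using IBM SPSS, version 25, and a $P < 0.05$ is considered significant".

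The same section bases the sample size on a "moderate effect size ($f = 0.25$) with 0.8 power to detect a difference between the two groups", for a design described as "With repeated measures ANOVA (2 groups x 3 time points"), and concludes that "a total of 37 participants including a 30% drop out rate were required for adequate power". Section E.1 plans "15 to 20 parent/infant dyads in each group", that is 30 to 40 in total.

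On timing, E.1 explains that parents cannot all keep the well-visit schedule, so "slightly flexible age ranges will be used for each data collection". Ages 2-4 months form one collection and 6-9 months another, and a parent who misses one visit is picked up at the next. E.1 also foresees unanswered surveys: the link is texted if the survey is not done at the visit, and one reminder follows. Infant age is taken from the chart for each window.

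**The concern.** The method does not fit the data that the protocol expects.

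- **Missing surveys.** Standard repeated measures ANOVA works on one row per dyad and deletes any row with a gap. This is a property of the procedure; the protocol does not state it. A dyad that answers two of three follow-up surveys contributes nothing. In a trial of 30 to 40 dyads, that discards data already collected.
- **Selective loss.** Complete-case results can be biased if loss depends on earlier feeding, and does so differently in the two arms. A likelihood-based mixed model tolerates loss that depends on observed responses.
- **Age.** Infants within one time point can differ by up to 2 months (2-4 window) or 3 months (6-9 window). Parents choose when solids start, so feeding can be expected to change with age inside these windows. The age spread goes into error, or into the group difference if attendance differs by arm. Demographic covariates do not address this, and a covariate in the standard ANCOVA is a single value per dyad, so it cannot carry an age that differs by visit.

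**Working it through.** **Inputs from E.2:** f = 0.25, power 0.80, significance level 0.05, 2 groups, m = 3 time points, 30% dropout, N = 37. **Assumed, because not stated:** correlation ρ = 0.5 between time points, sphericity, the three time points being the three follow-ups, and the patterns of missing surveys below.

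**1. The plan's own figure.** For the group-by-time interaction, λ = N·m·f²/(1 − ρ), with df = 2 and 2(N − 2).
- N = 28: λ = 28 × 3 × 0.0625 / 0.5 = 10.5, df 2 and 52, power 0.812. This is the smallest N reaching 0.80.
- 28 × 1.3 = 36.4, rounded up to 37. The stated figure reproduces.
- Dividing by the retained share instead gives 28 / 0.7 = 40.

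**2. Power when incomplete dyads are dropped.**
- 37 × 0.7 = 25.9, about 26 dyads: λ = 26 × 3 × 0.0625 / 0.5 = 9.75, df 2 and 48, power about 0.78.
- The table compares this with a mixed model on all observed visits, assuming an effect linear over visits. The low end has half of the incomplete dyads leaving after visit 1 and half after visit 2; the high end has each missing one survey.

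| Enrolled | Complete dyads | Complete-case power | Mixed-model power |
|---|---|---|---|
| 30 | 21 | 0.67 | 0.73 to 0.78 |
| 37 | about 26 | 0.78 | 0.82 to 0.87 |
| 40 | 28 | 0.81 | 0.85 to 0.89 |

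**3. Variance for the 12-month difference and for the mean of three visits.** Unit variance, ρ = 0.5, 70% complete, per enrolled dyad; the ratio is the same for the difference between arms.

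*Complete cases.* 12 months: 1/0.7 = 1.4286. Mean of three: [(1 + 2 × 0.5)/3]/0.7 = 0.9524.

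*Monotone dropout, 10% per visit (90%, 80%, 70% observed).* Each visit is estimated from its own data plus regression on earlier visits:
- Visit 1: 1/0.9 = 1.1111.
- Visit 2: 0.75/0.8 + 0.25 × 1.1111 = 1.2153. Covariance with visit 1: 0.5 × 1.1111 = 0.5556.
- Visit 3 (coefficients 1/3 and 1/3, residual variance 2/3): (2/3)/0.7 + (1/9)(1.1111 + 1.2153 + 2 × 0.5556) = 0.9524 + 0.3819 = 1.3343. Covariances with visits 1 and 2: 0.5556 and 0.5903.
- 12-month ratio: 1.4286/1.3343 = **1.07**.
- Mean of three: [1.1111 + 1.2153 + 1.3343 + 2(0.5556 + 0.5556 + 0.5903)]/9 = 0.7848. Ratio 0.9524/0.7848 = **1.21**.

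*Sporadic misses.* Each survey is returned independently with probability 0.7^(1/3) = 0.888. Summing the information over all patterns of observed visits gives 1.0867 at 12 months and 0.6959 for the mean. Ratios: 1.4286/1.0867 = **1.31** and 0.9524/0.6959 = **1.37**.

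**4. Share of dyads kept.** If each of three surveys is returned 85% or 90% of the time (assumed), 0.85³ = 0.61 or 0.90³ = 0.73 of dyads are complete.

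**5. Bias, as illustration only.** Suppose that in one arm alone the odds of dropout change by a factor of 1.65 (e^0.5) per SD of the earlier score, with no true effect. A simulation then gives a false complete-case difference of about 0.08 SD at 12 months. The standard error with 13 completers per arm is √(2/13) = 0.39 SD.

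**The case against.** The strongest reply is that the loss is already provided for. The 37 includes 30% dropout, and complete-case power falls only to about 0.78. This largely stands. The shortfall arises because 28 was multiplied by 1.3 rather than divided by 0.7; with 40 enrolled, complete cases reach 0.81. A reader might infer that the trial is seriously underpowered by its method of analysis. The figures do not support that at 37. The gap is wider if only 30 enrol, which E.1 allows.

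The protocol also works against missing surveys: the link is given at the visit and texted afterwards, incentives depend on completing surveys, and wide windows let a missed visit be made up. So the share of incomplete dyads may be lower than 30%. It may also be higher, since dropout is not the only way to miss a survey.

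On bias, a reader might infer that complete-case results are valid only if loss is unrelated to earlier feeding. That is too strong. If the same mechanism acts in both arms and there is no effect, the bias cancels from the group difference. Nothing in the protocol points to loss in one arm only, nor to an odds ratio of 1.65.

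On age, the windows are a reasoned design choice, and a mixed model with visit as a factor pools ages just as much. Only the age covariate addresses the pooling, and no magnitude can be given for it.

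Finally, this is described as a pilot, and missing-data rules may sit in an analysis plan not shown. But the protocol does more than leave a gap: it fixes a method, a significance level and a power target.

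**Conclusion.** The point holds as a modest one. The method fixed in E.2 discards partly observed dyads that the protocol itself leads one to expect, and takes no account of age within the windows. At 70% complete and correlation 0.5, the variance penalty at 12 months is 1.07 under monotone dropout and 1.31 under sporadic misses. The larger figures, 1.21 and 1.37, belong to the mean of three visits and should not be read as applying to the 12-month difference. E.2 speaks of dropout, which is nearer the monotone pattern and the smaller end. Complete-case power is about 0.78 at 37 enrolled and 0.67 at 30.

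Bias from selective loss is possible but unquantified; the 0.08 SD illustration rests on an assumed one-arm mechanism and is small beside a standard error of 0.39 SD. The cost of age pooling is also unquantified. All ratios and powers depend on the assumed correlation and missingness patterns. The point concerns feeding practices only, since E.2 names repeated measures ANOVA for nothing else.

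**What to change.** In E.2, replace repeated measures ANOVA/ANCOVA for feeding practices as follows:

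- **Continuous feeding scores:** a linear mixed model (SPSS MIXED) fitted by restricted maximum likelihood, with small-sample degrees of freedom where available. Fixed effects: group, visit, group-by-visit and age at assessment. Include all randomised dyads with at least one follow-up survey, and report the 12-month group difference with its 95% CI.
- **Yes/no feeding items,** to which a linear model is not suited: the logistic counterpart (SPSS GENLINMIXED).
- **Age at assessment:** derive it from date of birth, collected at enrolment, and the date of the survey or recall call. Chart age at the clinic visit will not serve, because a survey can be answered later by text link and recalls are separate calls.

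The cost is slightly more analysis work, and the survey or call date must be kept, which the protocol does not say is done. No new visits or software are needed. Dyads with no follow-up survey still contribute nothing.

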Texas Woman’s University’s IRB will rely on the North Texas Regional IRB and will sign an Institutional Authorization Agreement upon approval of the study by the North Texas Regional IRB . ([name], IRB Coordinator, [contact]; [contact])

5) *Laboratory methods and facilities* - N/A

6) *Estimated Period of Time to Complete the Study* –

Task	Year 1 (September 30, 2018-August 31, 2019) Quarters (3-months)				Year 2 September 30, 2019- February 28, 2020 Quarters (3-months)	
	9/30-11/30	12/1-2/28	3/1-5/31	6/1-8/31	9/1-11/30	12/1-2/28
Participant Recruitment	X					
Data Collection	X	X	X	X	X	
Data Analysis		X	X	X	X	
Manuscript Preparation						X

F. Human Subjects - Describe the characteristics of the research population:

1) *Sample Size*: 30-40 parent/infant dyads. Both parents may participate and receive separate text messages, but one compensation item will be provided per family.

2) Describe both *Inclusion / Exclusion Criteria*.

Inclusion criteria will be:

- Parents with age 18 and older. We don’t include parents younger than 18 because it is suspected that their concerns regarding feeding and sources of feeding advice may be different compared to adult parents.
- Healthy and term infants (born at 37 weeks or later) establishing care with the healthcare provider between 3-30 days of life and their infants (Parent/infant dyads).

- Parents must be able to speak and read English well. All researchers speak only English, thus we would like to pilot this in an English-speaking population first to make sure the messages are well crafted.
- Parents must have a mobile phone that can receive text messages and access the Internet.

Exclusion criteria will include:

- Infants with congenital anomalies, genetic disorders, or who develop failure-to-thrive during the intervention

3) Describe intended *gender, age range, intended racial and ethnic distribution*.

Both fathers and mothers are sought for participation. However, only one parent may fill out the questionnaires and will receive incentives for their participation. Participants must be adult parents of infants, but there is no upper age limit for participation. Because of the make-up of the clinic population, it is thought that about half of participants will be Hispanic to reflect the clinic population.

4) Identify the *source(s) from which you will obtain your study population*. All participants will be parents of infants and their infants attending the UNT-HSC Pediatric Clinic.

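### The protocol requires 37 participants for 0.8 power but lets recruitment stop at 30, and the 37 itself appears to be under-inflated for 30% dropout

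*Protocol*

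**What the plan says.** Section E.2 (Data Analysis and Data Monitoring) gives the sample size basis as "a moderate effect size ($f = 0.25$) with 0.8 power to detect a difference between the two groups". The design is described as "With repeated measures ANOVA (2 groups x 3 time points", and the section concludes that "a total of 37 participants including a 30% drop out rate were required for adequate power". The significance rule is that "a $P < 0.05$ is considered significant".

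The recruitment target appears in two other places. Section E.1 (Methods and Procedures) says "Thirty to 40 parent/infant dyads/triads of infants aged 3-30 days (15 to 20 parent/infant dyads in each group) will be recruited". Section F.1 (Sample Size) says "30-40 parent/infant dyads".

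The protocol does not give the number of completers needed, the formula used to allow for dropout, the correlation among repeated measurements, any sphericity assumption, or whether the calculation is for the group-by-time interaction or the between-group main effect.

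**The concern.** Two things look wrong. First, a number described as required for adequate power sits inside a recruitment range whose lower end is well below it. Recruitment could stop at 30 in full compliance with E.1 and F.1 and still miss the requirement in E.2.

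Second, the 37 looks like a completer count multiplied by 1.3. To keep n completers after losing 30%, n must be divided by 0.70. Multiplying by 1.3 leaves only 1.3 × 0.7 = 0.91 of the completers needed.

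At stake is how a null result is read. The protocol sets an efficacy objective and claims 0.8 power, so a null finding would be taken as coming from an adequately powered comparison when it may not be.

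**Working it through.** **Inputs from section E.2:** f = 0.25; power 0.80; significance level 0.05; k = 2 groups; m = 3 time points; dropout 30%; stated total 37. **From E.1 and F.1:** 30 to 40 dyads, 15 to 20 per group. **Assumed because not stated:** within-person correlation ρ = 0.5 (varied below), sphericity, and a test of the group-by-time interaction.

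**Step 1. The contradiction (no assumption needed).** 37 − 30 = 7, and 7/37 = 19%. The lower end of the range is 19% below the number called required.

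**Step 2. Reproducing the 37.** The noncentral F for the interaction has λ = f² × N × m / (1 − ρ), df1 = (k − 1)(m − 1) = 2 and df2 = (N − k)(m − 1) = 2(N − 2).

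- N = 27: λ = 0.0625 × 27 × 3 / 0.5 = 10.125, df2 = 50, power 0.795.
- N = 28: λ = 0.0625 × 28 × 3 / 0.5 = 10.5, df2 = 52, power 0.812.

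The smallest number of completers for 0.8 power is 28. The two ways to allow for 30% loss give:

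- 28 × 1.3 = 36.4, rounded up to 37, which is the stated figure.
- 28 / 0.70 = 40.

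**Step 3. Could 37 come from a correct division?** At ρ = 0.53 to 0.54 the need falls to 26 completers (power 0.804 to 0.813; 25 completers give 0.787 to 0.796), and 26 / 0.70 = 37.1. That gives 37 by rounding to nearest and 38 by rounding up. A correct division therefore cannot be excluded.

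**Step 4. Power at the numbers the protocol allows.**

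| Enrolled | Completers after 30% loss | Power, ρ = 0.3 | ρ = 0.5 | ρ = 0.7 |
|---|---|---|---|---|
| 30 | 21 | 0.52 | 0.67 | 0.89 |
| 37 | 25.9, taken as 25 | 0.60 | 0.76 | 0.94 |
| 37 | 25.9, taken as 26 | 0.62 | 0.78 | 0.95 |
| 40 | 28 | 0.66 | 0.81 | 0.96 |

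The correlation at which 0.8 power is just reached is about 0.62 for 21 completers, 0.525 for 26 and 0.49 for 28.

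**Step 5. Which effect is meant?** E.2 speaks of a difference between the two groups. Taken as the between-group main effect, λ = f² × N × m / (1 + (m − 1)ρ). At ρ = 0.5 this needs 86 completers (power 0.801), or 86 / 0.70 = 122.9, so 123 enrolled. Neither inflation of 86 comes near 37 (86 × 1.3 = 111.8), so at ρ = 0.5 the stated figure fits the interaction and not the main effect.

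**The case against.** The strongest reply is that the inflation error is inferred. The protocol prints neither 28 nor a factor of 1.3, and the exact match rests on ρ = 0.5, which it does not state. A small upward shift in ρ removes the shortfall at 37, and at ρ of about 0.62 or more even 30 enrolled reaches 0.8. In the other direction, at ρ = 0.4 the 28 completers from 40 enrolled give only 0.73, so 40 is not a safe number in itself. This stands. It makes every power figure conditional and leaves the multiplication by 1.3 as the likelier explanation, not an established fact.

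A reader might infer that the protocol definitely multiplied by 1.3 and that 0.8 power is therefore certainly missed at 37. The document does not support that. It shows no working, and a correct division at a slightly higher correlation comes within rounding of the same total.

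It can also be said that the shortfall at 37 is only 2 to 4 points, that 40 is already in the planned range, and that section B calls the trial a pilot. The first two points are fair and lower the severity. The pilot label does not settle the matter, because the same sentence proposes to compare efficacy and E.2 makes an explicit power claim. None of these replies touches the conflict between 37 and a range that starts at 30.

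**Conclusion.** The point holds in two parts of different strength.

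- **Certain:** the required 37 and the permitted minimum of 30 contradict each other by 7 participants. This depends on no assumption.
- **Probable:** the 37 is under-inflated, and 40 would be the matching figure. This rests on ρ = 0.5, sphericity and an interaction test.

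Under those assumptions the loss of power is small at 37 (0.76 to 0.78 against 0.80) and material at 30 (0.67, so the type II error rises from 20% to about 33%). At 40 the claim is met (0.81). Over correlations of 0.3 to 0.7, power runs from 0.52 to 0.89 at 21 completers, 0.62 to 0.95 at 26, and 0.66 to 0.96 at 28. This should be fixed, but it does not invalidate the design.

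**What to change.** In section E.2, state the assumed correlation, the sphericity assumption, the effect tested and the number of completers needed, then divide that number by 0.70. At ρ = 0.5 with the interaction test this reads 28 completers, 40 enrolled. Put the same single target in E.1, E.2 and F.1; 40 would be 20 per group, the top of the planned range.

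The figure of 40 should not be inserted without its assumptions, because a lower correlation or a main-effect test would need more.

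If a smaller number is kept, restate the power for it (at ρ = 0.5, about 0.67 for 30 enrolled and 0.76 to 0.78 for 37), or present the trial as a pilot and drop the claim of adequate power.

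The cost is a wording change in three places. Fixing the target at 40 commits the trial to 3 more dyads than 37 and 10 more than the present minimum, all within the range already planned.
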